8.2.2 PREGNANCY

Monitoring of pregnancies is not applicable to this study because pregnancy is an exclusion criterion and a pregnancy test is performed in all women of childbearing potential at screening. Owing to the nature of the study involving short (3-day) treatment with the study product in an inpatient setting, it is not possible for women to become pregnant during treatment and for there to be any fetal exposure to the study product.

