Patients diagnosed with ARDS or PNA will undergo screening during which informed consent will be obtained and eligibility assessed. Up to 7 or 14 days may elapse between confirmation of PNA or ARDS diagnosis respectively and administration of the first infusion of study product. Patients will be dosed once per day for 3 consecutive days (Day 0, 1, 2). In Arm 1 (Dose Escalation), patients were monitored for 7 days after the first Descartes-30 infusion (unless they are discharged from the administering unit prior to Day 7) with a safety review on Day 7 (or last day in the administering unit, whichever comes earlier) to determine whether the next patient in the trial can be dosed. In Arm 2 (Dose Expansion), patients will be enrolled consecutively to receive treatment on Day 0, 1, and 2 at a dose up to the MTD determined in Arm 1. For both Arms, there will be an optional visit on Days 14 and 21 and a mandatory visit on Day 28. Long-term follow-up will occur at Day 90 (in-person or telephone contact).

Study Intervention:

The study product will be manufactured from qualified allogeneic donors under GMP standards. After the product passes Quality Control, it will be shipped to the study site for storage. Patients will receive the first dose of Descartes-30 cells via intravenous administration within 14 days of diagnosis of ARDS or within 7 days of diagnosis of PNA. Patients will receive two more infusions over the following 2 days unless they meet the criteria for holding dose or discontinuing study treatment.

In the dose escalation arm (Arm 1), the following doses of Descartes-30 cells are planned:

- Dose Level 1: 100 million cells administered on Days 0, 1 and 2
- Dose Level 2: 300 million cells administered on Days 0, 1 and 2
- Dose Level 3: 600 million cells administered on Days 0, 1 and 2

- Dose Level 4: 1200 million cells administered on Days 0, 1 and 2

An additional 12 patients per cohort (ARDS or PNA) may be enrolled at a dose up to MTD.

Study Duration: 30 months

Participant Duration: 3 months

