2.1 RISK/BENEFIT ASSESSMENT

Descartes-30 consists of allogeneic human MSCs modified by introduction of mRNA to transiently secrete recombinant human Dnase1 and human Dnase1L3. Allogeneic human MSCs for therapeutic use have been well characterized and are currently administered in over 100 COVID-19-related clinical trials. Both Dnase1 and Dnase1L3 are normally expressed and found in the plasma of healthy persons. In the extracellular milieu, they do not appear to have any endogenous target except for extracellular DNA. Furthermore, both Dnase1 and Dnase1L3 are macromolecules of sufficient bulk that they do not cross the plasma and nuclear membrane of healthy cells.

Recombinant human Dnase1 has an excellent safety profile and was approved by the FDA nearly 30 years ago for inhaled administration in the treatment of cystic fibrosis (i.e., PULMOZYME®). Descartes-30 cells are engineered with mRNA that cannot modify the cell genome, eliminating the risk of gene transfer-induced transformation. No viral particles or antibiotics are used in manufacturing. The final product is confirmed to be free of residual DNA, further reducing the risk of integration. The Dnases are secreted temporarily, and their expression wanes over several days, which is expected to avoid the risk of long-term toxicity.

Because Dnases have very short half-lives in human serum, a cell-based therapy is an ideal delivery system that bypasses the need for frequent drug administration to achieve therapeutic levels of exposure. Furthermore, as MSCs naturally home to pulmonary vascular sites, Descartes-30 cells are expected to travel to the sites of NET formation that underlie ARDS and PNA, conferring spatially targeted delivery. The natural immunomodulatory properties of MSCs can further inhibit ARDS and PNA-related inflammation⁵⁸. Thus, targeted systemic delivery of Dnase-producing MSCs can benefit patients with ARDS and PNA through several mechanisms:

1. decrease airway mucus viscosity through breaking down extracellular DNA, thus improving airway clearance;
2. decrease/prevent microvascular thrombus, thus improving oxygenation;
3. reduce local tissue exposure to immune-mediated injury caused by NETs; and
4. inhibit inflammation directly by MSCs.

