4.4 DOSE ESCALATION RULES

A minimum of three patients will be dosed at each dose level. In the dose escalation arm, there will be a minimum of 7 days between each patient's first cell infusion. At the time a patient is diagnosed with ARDS, the clinic will contact the sponsor who, by default, will assign the patient to the next slot in the active dose level. Patients will receive three doses of Descartes-30 cells on Days 0,1 and 2. On Day 7 or last day in ICU, whichever comes earlier, the Principal Investigator will review the clinical data with the Medical Monitor and authorize the next patient's infusion if there is no safety concern. The selection of Day 7 for safety review is based upon preclinical data demonstrating that Dnase expression wanes over 7 days. Furthermore, the study will not proceed to the next dose level until: 1) at least 3 patients in the previous dose level have been observed through Primary Safety Review; 2) no study stopping rules have been triggered; and 3) the medical safety monitor has reviewed the cumulative safety data and concluded and documented that the next Dose Level may be initiated.

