6.4 PRIMARY SAFETY REVIEW (DAY 7)

Primary Safety Review is on Day 7 or on last day of stay in the administering unit, whichever comes earlier. In Arm 1, upon completion of Primary Safety Review assessments, the Principal Investigator and the Medical Monitor will review the data.

- Physical Exams: Abbreviated, targeted physical examinations (i.e., assessments of the skin, respiratory, cardiovascular system, and abdomen (liver and spleen), will be performed at time points specified in the Schedule of Activities (Section 1) and will be based on the subject's clinical status and what the clinic staff deem is appropriate.
- Concomitant medications
- Clinical End-point Assessment includes: Survival (Y/N), On mechanical ventilation (Y/N), In ICU (Y/N), In Hospital (Y/N), Use of anti-coagulation (drug, dose, intent: prophylaxis vs therapeutic), WHO Ordinal Score (See Appendix D for scale). If patient is in ICU then the following assessment will be completed: Sequential Organ Failure Assessment (SOFA), PaO₂/FiO₂, following ventilation parameters (as applicable): type of ventilation (CPAP, BiPAP, or intubation)/ ventilation rate/ pulse/ tidal volume/ positive end-expiratory pressure (PEEP), recording of vasoactive drugs and renal support, recording of supportive interventions that can impact clinical endpoints (use of prone ventilation, use of paralytics, use of pulmonary vasodilators, use of corticosteroids, use of oral decontamination and raising the head of the patient to at least 30° to prevent ventilator-associated pneumonia)
- Vital Signs: include core temperature, mean arterial pressure (mmHg), pulse (beats/min), respiratory rate (breaths/min).
 - The same method for assessing temperature should be used at all visits until patient is discharged from the administering unit, if possible.

- CBC with differential: Samples should be taken in the morning between 04:00 and 10:00 using the values closest to 10:00 (mandatory for Arm 1, only if done as part of standard of care for Arm 2).
- Serum chemistry (mandatory for Arm 1, only if done as part of standard of care for Arm 2):
 - Samples should be taken in the morning between 04:00 and 10:00 using the values closest to 10:00.
 - Chemistry includes Glucose, Ca, Mg, Phos, ALP, Albumin, Total Protein, Total Bilirubin, K, Na, Cl, HCO₃, BUN, Cr, ALT, AST, LDH, Amylase.
- CRP, ferritin, D-Dimer (mandatory for both Arms).

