7.1.2 DOSING AND ADMINISTRATION

7.1.2.1 PRE-INFUSION MONITORING AND DELAY OF CELL INFUSION

[figure not shown]
Infusions can be delayed up to 96 hours based on PI discretion. Prior to all Descartes-30 infusions, patients should be observed for 2 hours (\pm 30 min) to document their stability by meeting the following parameters and based on PI's best clinical judgement:

1. Patient is not requiring a change in ventilator settings
2. Stable use of vasopressors if the patient required vasopressors for blood pressure support.
Stable use is defined as increasing no more than 50% of baseline recorded at initiation of monitoring.

During 2-hour monitoring, following parameters should be recorded at least every 30 min: ventilation variables [type of ventilation (CPAP, BiPAP, or intubation), ventilation rate, pulse, tidal volume, positive end-expiratory pressure (PEEP)], recording of vasoactive drugs and renal support and vital signs [include core temperature, mean arterial pressure (mmHg), pulse (beats/min), respiratory rate (breaths/min)]. If patients do not meet stability criteria for 2 hours, infusion can be delayed for up to 96 hours. If infusion is delayed, the patient will be periodically monitored to assess stability. If infusion is delayed more than 96 hours due to medical instability, patients will come off study treatment. Infusions can also be delayed up to 96 hours in case of a holiday or by PI's discretion.

Patients experiencing toxicities that are probably or definitely related to Descartes-30 will have their next Descartes-30 dose delayed until these toxicities have resolved to at least Grade 2, unless in the documented opinion of the site Principal Investigator and the medical monitor it is reasonable to proceed. During this period, patients will be assessed to record adverse events and decide whether the patient meets criteria for cell infusion. The discussions between the Medical Monitor and site Principal Investigator will be documented. If a dose is delayed for more than 96 hours, the patient will come off study treatment.

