8.2 RECORDING OF ADVERSE EVENTS

8.2.1 ADVERSE EVENT RECORDING

The adverse event recording period for this study starts after patient or legal representative signs consent and ends at Day 90 visit or when patient comes **off-study based on criteria in Section 8.4**. For SAE and SUSAR, reporting period starts with first Descartes-30 infusion and ends 7 days after last infusion. After 7 days, an AE (only in Arm 2), SAE (both Arms) or SUSAR (both Arms) is **only reported if it is probably or definitely attributed to Descartes-30 infusion**. At each contact with the subject during the adverse event recording period, the Investigator or his/her designee must seek information on adverse events by specific questioning and, as appropriate, by examination. Information on all adverse events should be recorded immediately in the source document, and in the appropriate adverse event module of the case report form (CRF). All clearly related signs, symptoms, and abnormal diagnostic procedures results should be recorded in the source document, though it should be grouped under one diagnosis.

All adverse events should be treated appropriately. If a concomitant medication or non-drug therapy is given, this action should be recorded on the Adverse Event CRF. Adverse events should be entered into the e-CRF system within 3 working days from the knowledge of the event took place. Once an adverse event is detected, it should be followed until its resolution or until it is judged to be permanent, and assessment should be made at each visit (or more frequently, if necessary) of any changes in severity, the suspected relationship to the study treatment, the interventions required to treat it, and the outcome.

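### Section 8.2.2 sets pregnancy monitoring aside because fetal exposure is held to be impossible; the protocol's own test schedule, expression time and discharge provisions do not support this, and nothing requires a pregnancy found by Day 90 to be reported

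*Combined protocol and SAP*

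**What the plan says.** Section 8.2.2 (Pregnancy) opens with the rule: "Monitoring of pregnancies is not applicable to this study because pregnancy is an exclusion criterion". It adds that women of childbearing potential are tested at screening. It then argues from the short, three-day inpatient treatment that "it is not possible for women to become pregnant during treatment and for there to be any fetal exposure to the study product".

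Other parts of the protocol bear on this:

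- **Testing.** The schedule of activities (Section 1) marks the pregnancy test at Screening only. Sections 6.2 to 6.6 do not list it again.
- **Duration of expression.** Section 4.4 bases the Day 7 review on "preclinical data demonstrating that Dnase expression wanes over 7 days". Section 2.1 says of the enzymes that "their expression wanes over several days".
- **Discharge.** Footnote l of the schedule, attached to the Day 3-6 column among others, lets assessments be omitted once the patient has left hospital.
- **Reporting.** Under Section 8.2.1, AE recording runs from consent to Day 90. SAEs and SUSARs are reported from the first infusion to 7 days after the last. After that, an Arm 2 AE, or an SAE or SUSAR in either arm, is "only reported if it is probably or definitely attributed to Descartes-30 infusion".

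**The concern.** The sentence in 8.2.2 joins two claims: that conception cannot occur during treatment, and that there can be no fetal exposure. The first is reasonable for three inpatient dosing days. The second does not follow from it, for two reasons. A woman may already be pregnant, undetected, when she is infused. A woman who conceives after discharge may do so while the cells are still expressing enzyme.

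Safety is the primary objective, and patients are followed to Day 90. If an exposed pregnancy came to light in that time, no stated rule would bring it to the sponsor or have its outcome followed. The safety record would then be incomplete on an outcome that the plan has declared impossible. The handling is also uneven. For malignancy, which Section 7.2.2.4 calls a theoretical risk, patients are to report a diagnosis even after they have left the study.

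**Working it through.** The plan gives no figure to reproduce. The check compares its statements and uses simple day counts.

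**Step 1. Does the screening test exclude a pregnancy already present?** There is one blood or urine test, and footnote j of the schedule allows screening and the first infusion on the same day. The documents give no detection limit. I assume only that such a test cannot detect a pregnancy from the moment of conception. On that assumption, a very early pregnancy can pass screening and be exposed to all three infusions. This route does not depend on the expression time or on discharge.

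**Step 2. Can expression outlast the hospital stay?** Inputs:

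- Last infusion on schedule: Day 2 (Synopsis, Study Design)
- Waning time: k = 7 days, preclinical (Section 4.4)
- Hospital discharge allowed for: day d = 3 to 6 (Section 1, footnote l)

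End of waning = 2 + k = 2 + 7 = Day 9.

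Days between discharge and end of waning = 2 + k − d:

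| Discharge day d | Gap with k = 7 | Gap is above zero when |
|---|---|---|
| 3 | 2 + 7 − 3 = 6 days | k is more than 1 day |
| 6 | 2 + 7 − 6 = 3 days | k is more than 4 days |

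Section 2.1 speaks only of several days. With a Day 3 discharge any k above 1 day still leaves a gap; with a Day 6 discharge k must exceed 4 days.

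**Step 3. Would any rule require a report?**

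| Route | What the protocol provides |
|---|---|
| Pregnancy reporting (8.2.2) | None; monitoring is not applicable |
| SAE list (8.1.3) | Names neither pregnancy nor congenital anomaly |
| SAE/SUSAR, both arms (8.2.1) | Reported up to 7 days after the last infusion (Day 2 + 7 = Day 9); later only if probably or definitely attributed |
| AE, Arm 2 (8.2.1) | After 7 days, only if probably or definitely attributed |
| AE, Arm 1 (8.2.1) | Recorded to Day 90 without that limit, but pregnancy is not named as an AE (8.1.1) |

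On schedule, the attribution condition covers Day 10 to Day 90, which is 90 − 10 + 1 = 81 days. It applies to AEs in Arm 2, about 24 of about 36 patients by the Synopsis. An investigator who has read in 8.2.2 that exposure cannot happen has little basis for attributing an event to the product.

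**The case against.** The strongest defence is that 8.2.2 is a reasoned choice and speaks of treatment, meaning the inpatient dosing days. Waning over 7 days is a decline and not full exposure for 7 days; the figure is preclinical, and Section 4.4 uses it only to justify the Day 7 review. Section 2.1 adds that Dnases have very short half-lives in serum. Discharge and conception within days of ARDS or severe pneumonia is improbable. All of this stands as a reason to expect very few events. It does not rescue the denial of any fetal exposure, and it does not answer the early-pregnancy route in Step 1.

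A reader might also infer stronger points, which the documents do not support:

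- **That delayed infusions widen the gap.** Section 7.1.2.1 says "Infusions can be delayed up to 96 hours based on PI discretion". But 8.2.2 describes treatment as inpatient, so a delay to the last infusion moves the last inpatient dosing day and the end of waning together. The tail is still about 7 days.
- **That leaving the unit means leaving hospital.** Section 6.4 says "Primary Safety Review is on Day 7 or on last day of stay in the administering unit, whichever comes earlier". That concerns the administering unit. The support for early hospital discharge is footnote l.
- **That pregnancy is excluded because exposure is a known worry.** Section 5.2 lists the exclusion without a reason.
- **That 8.2.2 forbids collecting pregnancies, or that they would certainly go unreported.** It says that monitoring does not apply; it prohibits nothing. Arm 1 AEs are recorded to Day 90, an attributed event is reportable in either arm, and a complication of pregnancy could meet the AE definition.

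**Conclusion.** The concern holds as a minor gap in safety reporting. The absolute statement in 8.2.2 is not supported by the protocol's own provisions: a single test at screening, expression that wanes to about 7 days after the last infusion, and possible hospital discharge about 3 to 6 days before that point. No passage requires a pregnancy found in follow-up to be reported or its outcome followed.

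The documents give no pregnancy rate, so the number of events cannot be calculated; in about 36 severely ill patients it will be very small and may well be zero. No estimate, test or escalation decision changes. The conclusion rests on three assumptions: that a screening test can miss a very early pregnancy, that the preclinical waning time is a fair guide to the period of possible exposure, and that no separate safety form or consent document, which I have not seen, already sets a pregnancy reporting rule.

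**What to change.** In Section 8.2.2:

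1. Delete the statement that fetal exposure is not possible.
2. Reconcile the period of possible exposure with Section 4.4 and with the discharge provisions in the schedule of activities.
3. Require that any pregnancy identified during the existing follow-up to Day 90 be reported to the sponsor and followed to outcome, whether or not it is attributed to the product.
4. Add one question on pregnancy for women of childbearing potential at the Day 90 contact, where AE review already takes place (Section 6.6). The Day 28 visit cannot be relied on for this, because Section 6.5 lets it fall on the day of hospital discharge.

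The cost is one reworded paragraph, a pregnancy report form and one question at an existing contact. The downside is a little reporting work in a very rare case, including some pregnancies conceived after any plausible exposure. No dose, eligibility rule or analysis changes.

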8.3 SAE AND SUSAR REPORTING

To ensure patient safety, every SAE and SUSAR, regardless of suspected causality, occurring during the adverse event reporting period defined in Section 8.2.1 must be reported to the Sponsor within 24 hours of learning of its occurrence. Recurrent episodes, complications, or progression of the initial SAE must be reported as follow-up information is received. An SAE occurring at a different time interval or otherwise considered completely unrelated to a previously reported one should be reported separately as a new event.

8.3.1 STUDY SPONSOR NOTIFICATION

Any SUSAR and SAE as defined in Section 8.1.3 and Section 8.1.4 must be reported to the Sponsor by **fax within 24 hours** of knowledge of the event. SUSARs and SAEs should also be discussed via email or telephone contact with the Sponsor Medical Monitor. To the extent possible, adverse events should be recorded as a diagnosis. Do not list symptoms if a diagnosis can be assigned. At the time of the initial notification, a serious adverse event (SAE) report form should be filled. The following information will be collected in the form:

- subject identifying information;
- a description of the event (if there is a diagnosis, it should be included);
- date of onset;
- current status;
- whether study treatment was discontinued;
- reason why the event is classified as serious;
- investigator assessment of the association between the event and study treatment;
- concomitant medications when the event happened; and
- narrative summary of the event.

Follow-up information on this event should be reported when received. The follow-up information should describe 1) whether the event has resolved (with or without sequelae) or continues; 2) if and how it was treated; and 3) whether the patient continued or withdrew from study participation.

8.3.2 IRB NOTIFICATION

Information that indicates a change to the patient risks or potential benefits of the research, in terms of severity or frequency, should be communicated to the IRB in the following scenarios:

- safety monitoring indicates that a particular side effect is more severe, or more frequent than initially expected;
- change in FDA safety labeling or withdrawal from the marketing of a drug, device, or biologic used in a research protocol;
- breach of confidentiality;
- change to the protocol taken without prior IRB review to eliminate an apparent immediate hazard to a research participant;
- complaint by a participant when the complaint indicates unexpected risks, or the complaint cannot be resolved by the research team; or
- protocol violation (meaning an accidental or unintentional deviation from the IRB approved protocol) that in the opinion of the investigator placed one or more participants at increased risk or affects the rights or welfare of subjects.

Deaths that occur during the study should be reported within the IRB-specified time frame. For reportable deaths, the initial submission to the IRB may be made by contacting the IRB Director or Associate Director. The AE/Unanticipated Problem Form is required as a follow up to the initial submission.

8.3.3 FDA NOTIFICATION

The Sponsor is required to report certain study events in an expedited fashion to the FDA. These written notifications of adverse events are referred to as IND safety reports. The sponsor must report an IND safety reports as described in:

<http://www.fda.gov/downloads/Drugs/GuidanceComplianceRegulatoryInformation/Guidances/UCM227351.pdf>

The following describes the safety reporting requirements by timeline for reporting and associated type of event:

- **within 7 Calendar Days** any study event that is unexpected, fatal or life-threatening suspected adverse reaction; or
- **within 15 Calendar Days** any study event that is unexpected, suspected adverse reaction that is serious, but not fatal or life-threatening -or- a previous adverse event that was not initially deemed reportable but is later found to fit the criteria for reporting, any finding from tests in laboratory animals that suggest a significant risk for human subjects including reports of mutagenicity, teratogenicity, or carcinogenicity or reports of significant organ toxicity at or near the expected human exposure.

